4.0 RESEARCH DESIGN

4.1 SUMMARY OF TRIAL DESIGN

Summary of Trial Design: This study will enroll evaluable patients undergoing surgical resection of malignant, grade IV gliomas in both of two groups: those with newly diagnosed GBM and those with recurrent GBM. Patient, in each group (primary vs recurrent GBM) will be randomized to one of 2 levels of ALA dose (10 and 20 mg/kg) to be given orally at 3 hours prior to anticipated midpoint of surgery.

4.2 RANDOMIZATION

Patients who have consented to this protocol will be randomly assigned to one of two ALA dose groups (Table 3). Randomization will be stratified by whether the tumor is newly diagnosed (i.e. *de novo*) or recurrent. The data center will prepare sealed, opaque envelopes with the randomized assignment to ALA dose and administration time and notify the pharmacy of the trial site so that so that the correct ALA dose can be prepared.

Neurosurgeons and investigators responsible for determining pathologic characteristics, for quantifying fluorescence images, for extracting chemical PpIX, for co-localizing fluorescence images with MR images will be blinded to the ALA dose and administration time. In case of emergency, such as toxicity or allergic reaction attributable to the drug, the research pharmacist on call will break the blind and inform the PI and the physician responsible for clinical management.

A safety monitoring board has been developed at the Case Comprehensive Cancer Center at Case Western Reserve University. Also, forms will be filled out by the surgeon postoperatively on a daily basis, the patient's surgeon will report any adverse effects. In addition to specific signs and symptoms, liver function tests will be ascertained at 48

hours and, if abnormal, these tests will be continued on a twice-weekly basis until they peak and then at weekly intervals thereafter to resolution. In the case of any adverse event, the patient will be examined by the study physician and appropriate medical action taken.

4.3 DSMB AND DSTC

4.3.1. Data Safety Monitoring Board (DSMB)

The Data Safety Monitoring Board for this study is:

The Standing Data Safety Monitoring Board of the Case Comprehensive Cancer Center, Case Western Reserve University, School of Medicine.

4.3.3 Site for surgical resection and fluorescence imaging

Surgical resection and fluorescence imaging will be performed by neurosurgeons at University Hospitals Cleveland Medical Center.

Image processing for quantification of the fluorescence signal and clinical support, training and maintenance for the fluorescence imaging devices will be provided by [name] lab.

In addition, a dedicated person will be assigned that is responsible for on-site clinical support, data/sample management, data/sample transfer to [name] lab, and on-site maintenance and storage of the fluorescent imaging device.

4.4 PRE-OPERATIVE PROCEDURES

4.4.1 PATIENT INFORMED CONSENT

Patients will enter this study on a voluntary basis. Enrolled patients receive an information package that includes an informed consent form. This package will inform the patient about the objectives of the study, the procedures that will be used, the potential risks involved, and the procedures that they should undertake to avoid possible photosensitivity reactions. At the time of obtaining consent for surgery, the attending surgeon or their delegate will obtain informed consent for this trial.

4.4.2 LIGHT SENSITIVITY PRECAUTIONS

Before ALA administration, patients will be given verbal and written instructions for protection from sunlight by the staff surgeon or his delegate (see Section 4.7.1). It should be noted that these patients are hospitalized following surgery, so that there is in practice a very small possibility of their being exposed to bright sunlight outdoors. Nursing staff in the recovery room and on the ward will be instructed regarding the need to avoid accidental exposure to bright light in the first 24 hours.

4.4.3 .PATIENT GROUPS AND NUMBERS AND ALA DOSE

This clinical trial has ALA dose at 2 levels (10 and 20 mg/kg) and ALA administration time at 1 time point (3h). Consenting patients scheduled for surgery will be assigned to primary or recurrent arm based on clinical presentation, are then randomly assigned to one of two groups (for dose assignment) within each of the two arms of the study. Sample sizes of the 4 patient groups with two ALA dose levels are listed in the table below:

Table 3: Study Design and Sample Size

	Administration Time	
	3 hours New D _x	3 hours Recurrent D _x
10 mg/kg	30	30
20 mg/kg	30	30

For both patients with new and recurrent disease, biopsies will be taken at up to six sites identified by the surgeon: in the tumor center, tumor edge, area surrounding the tumor (if safe), areas seen to fluoresce intraoperatively and an area with MR enhancement outside

the tumor region (if this can be accomplished safely). Prior to collecting these biopsies readings will be taken at the biopsied location with the PpIX point probe by the surgeon. For each of the 6 biopsies, they will be divided into 3 parts and distributed for further analysis as follows: one portion will be sent to the pathologist for assessment of tumor percentage, one portion will be evaluated by the Division of Biophysics at the University of Toronto for PpIX concentration and the other for assessment of fluorescence.

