4.4.2 SURGICAL TREATMENT

During surgery, the intraoperative fluorescence observations and PpIX concentration measurements will be taken by the surgeon and recorded by research personnel. The surgical site will be illuminated with UV/blue light in the wavelength range of 350-490nm with an irradiance of 20-40 mWcm⁻². A fluorescence image will be taken using a commercially available operating room microscope. A white-light image will also be taken using the same microscope in non-fluorescence mode. Each tissue biopsy will be taken at the discretion of the operating surgeon (the biopsy location on the fluorescence image will be recorded) and divided in 3 parts that will be analyzed by histopathology, fluorometry, and fluorescence microscopy. At each site, the position of the biopsy in the tumor bed will be determined by frameless stereotaxy using an Optical Tracking System (OTS) for correlation with pre- and post-operative CT and/or MRI scans. Biopsies of 50mg or less are taken with biopsy forceps .

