4.4.3.1 BULK TUMOR MEASUREMENTS

1. Under white light illumination, the surgeon will identify biopsy sites of tumor and normal tissue with a probe and corresponding white-light and fluorescence images will be taken.
2. A biopsy will be taken of each of the sites identified under white light illumination and under fluorescence imaging.

Additionally, the location of the biopsies will be determined with an Optical Tracking System for post-operative correlation with pre- and post-operative CT and/or MR-scans.

The exact step-by step operating room procedures for these intra-operative measurements are described in Appendix III, Section 12.

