5.2 DATA ANALYSIS

5.2.1 FLUORESCENCE INTENSITY LEVELS VS. HISTOPATHOLOGY

The data sets will be collated into the 4 study groups (2 ALA doses and 2 study arms-- i.e., newly diagnosed and recurrent diagnosis) for analysis purposes.

Histopathology of the 1st part of the biopsies, performed by a single experienced neuropathologist (**i.e., [name]**) will be used as the gold standard. The white-light, fluorescence images, and intra-operative PpIX concentration readings will be compared to assess the sensitivity and specificity for biopsy-confirmed visible tumor.

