6.0 STATISTICAL PARAMETERS

6.1 PATIENT DATA SET

For each patient the following data will be captured for analysis (collection timing in parens):

1. Patient demographic information (at enrollment).
2. Tumor/normal tissue classification for each biopsy by the neurosurgeon (intra-operatively).
3. Histology report on 1st part of biopsies (one to several weeks post-operatively).
4. PpIX extraction assay 2nd part of biopsies (one to several months post-operatively).
5. Confocal microscopy fluorescence images on 3rd part of biopsies (one to several months post-operatively).
6. White light images of biopsy sites (i.e. of the tissue area around the biopsy location; intra-operatively).
7. Fluorescence images of biopsy sites over an area sufficient to clearly demarcate the region of interest (intra-operatively).
8. PpIX concentration at biopsy site.
9. Frameless stereotaxy coordinates of biopsies (intra-operatively).
10. Magnetic Resonance appearance of biopsy at coordinates taken in #8 (one to several weeks post-operatively).
11. Magnetic Resonance image volumes (i.e., pre-, intra-, and post-operative; one to several weeks post-operatively).

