8.0 STATISTICAL CONSIDERATIONS

8.1 STATISTICAL ANALYSIS PLAN

Primary objective: We will assess 2 doses of 5-ALA, 10mg/kg and 20mg/kg, to determine the optimum ALA dose in terms of both sensitivity and specificity for residual tumor. The endpoint will be correspondence between intensity of *in vivo* fluorescence and PpIX concentration and the pathologist's quantification of tumor in biopsy specimens, e.g. percent tumor present. Receiver operating characteristic (ROC) curves will be calculated for each of the 2 combinations of ALA dose to estimate a level of fluorescence that distinguishes residual tumor from normal tissue with large true positive fraction (TPF) and small false positive fraction (FPF). A joint 95% confidence region for TPF FPF will be calculated, using $\alpha^*=1-\sqrt{1-\alpha}=0.975$ and univariate confidence limits for the individual probabilities. Having chosen the cut-points for each of the 4 combinations, positive and negative predictive values and diagnostic likelihood ratios will be calculated to describe the characteristics of each [18].

To compare the test characteristics of each ALA dose and to assess how the test characteristics are affected by demographic, disease, and surgical characteristics we will

fit multivariable generalized mixed models to tumor and normal biopsy specimens using robust standard errors to account for the correlation of samples taken from the same individual.

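### Section 4.4.3 lists fluorescing areas among the biopsy sites while 8.2 assumes sites set by location; 5.2.1, 6.1, 8.1 and 8.2 do not separate the two, so the 80% is not established for the sampling described

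*Combined protocol and SAP*

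**What the plan says.** The sections describe the sampled sites differently.

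- **Section 4.4.3 (Patient groups and numbers and ALA dose):** up to six sites identified by the surgeon. After tumor center and edge, the list continues with "area surrounding the tumor (if safe), areas seen to fluoresce intraoperatively and an area with MR enhancement" outside the tumor region.
- **Section 4.4.2 (Surgical treatment):** "Each tissue biopsy will be taken at the discretion of the operating surgeon".
- **Section 4.4.3.1 (Bulk tumor measurements):** step 1 reads "Under white light illumination, the surgeon will identify biopsy sites of tumor and normal tissue with a probe". Step 2 reads "A biopsy will be taken of each of the sites identified under white light illumination and under fluorescence imaging". The section then adds: "The exact step-by step operating room procedures for these intra-operative measurements are described in Appendix III, Section 12".
- **Section 8.2:** six sites by location (two center, two edge, two adjacent normal), averaging three tumor-positive and three tumor-negative by pathology.

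The accuracy analyses do not distinguish how a site was chosen. In 5.2.1 the images and intra-operative PpIX readings "will be compared to assess the sensitivity and specificity for biopsy-confirmed visible tumor". In 8.1, ROC curves are calculated "to estimate a level of fluorescence that distinguishes residual tumor from normal tissue". Also in 8.1, under the secondary objective, sensitivity is defined as the chance of observable fluorescence when tumor cells are present. Section 8.2 counts a surgeon's score of 1 or higher as positive and compares the doses on the Youden index. The per-biopsy items in 6.1 include the surgeon's tumor/normal call, images, PpIX, MR appearance and "Frameless stereotaxy coordinates of biopsies", but not the reason for choosing the site.

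**The concern.** If a specimen is taken because the site visibly fluoresces, the index test has decided whether that specimen enters the data. Under the score rule such a site can only be a true positive or a false positive. Pooling these sites with the others raises apparent sensitivity and lowers apparent specificity unless every one contains tumor. The net effect on the Youden index can have either sign or be close to zero. Robust standard errors handle correlation within a patient; they do not correct selection on the test result.

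The primary dose comparison is at stake. With pooling, each dose's estimates no longer describe its accuracy at sites chosen independently of fluorescence, and the distortion need not be equal at the two doses. The 80% in 8.2 was derived without any such sites. Under the ROC or probe cut-points of 8.1 and 5.2.1 a chosen site can still fall below the cut-point, so there the selection is only partial.

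**Working it through.** **Inputs from 8.2.** The 12 sensitivity/specificity rows of its Table 1; a Youden difference of 0.10; n=30 per dose and stratum; three tumor and three normal samples per patient; ρ of 0.1 or 0.2; variance p(1−p)(1+2ρ)/(3n).

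**Step 1: the plan's own figure.** P(correct) = Φ(difference / √variance). For row 1 (0.75/0.70 against 0.60/0.75), the sum of p(1−p) is 0.1875 + 0.21 + 0.24 + 0.1875 = 0.825.

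- Required n at ρ=0.2: 0.8416² × 0.825 × (1.4/3) / 0.10² = 27.3; the table prints 27.
- At n=30: variance 0.825 × 1.4/90 = 0.01283, so Φ(0.10/0.1133) = 0.811.

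All 24 table entries reproduce to within one patient. At n=30, P(correct) is 0.820–0.844 (ρ=0.1) and 0.802–0.825 (ρ=0.2). The claim holds for location-defined sites, with little slack at ρ=0.2.

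**Step 2: pooling fluorescence-chosen sites.** The documents give neither the number of targeted sites, k, nor their tumor share, q. Assumptions: the same k at both doses, no overlap with other sites, the other 6−k sites half tumor, and q either each dose's positive predictive value (PPV) at 50% prevalence or a common 0.71–0.95. With w = (6−k)/2:

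- apparent sensitivity = (se·w + kq) / (w + kq)
- apparent specificity = sp·w / (w + k(1−q))
- variance of each = p(1−p)(1+(m−1)ρ)/(mn), where p is the apparent value and m the resulting tumor or normal samples per patient.

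Row 1, k=1, q at PPV:

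- 20 mg/kg: q = 0.75/1.05 = 0.714. Sensitivity 2.589/3.214 = 0.806; specificity 1.75/2.786 = 0.628.
- 10 mg/kg: q = 0.60/0.85 = 0.706. Sensitivity 2.206/3.206 = 0.688; specificity 1.875/2.794 = 0.671.
- The Youden difference shrinks from 0.10 to 0.075 and P(correct) is 0.744. With k=2 they are 0.054 and 0.682.

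In the row 0.75/0.70 against 0.70/0.85, the difference of −0.10 grows to −0.135 (k=1) and −0.159 (k=2).

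Ranges over all rows and the assumed q, at n=30 and ρ=0.2:

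| Targeted sites per patient | 20 mg/kg better (6 rows) | 10 mg/kg better (6 rows) |
|---|---|---|
| 0 (plan) | 0.80–0.81 | 0.81–0.83 |
| 0.5 (partial overlap) | 0.75–0.79 | 0.80–0.88 |
| 1 | 0.70–0.78 | 0.79–0.92 |
| 2 | 0.60–0.75 | 0.76–0.96 |

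At ρ=0.1 the 20 mg/kg column becomes 0.82–0.83, 0.77–0.81, 0.71–0.80 and 0.61–0.77. A beta-binomial simulation at ρ=0.2 with targeted sites always positive gives similar ranges: 0.71–0.79 and 0.61–0.79 when 20 mg/kg is better, and 0.80–0.93 and 0.79–0.98 when 10 mg/kg is better (one and two sites).

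**Step 3: unequal counts.** Fluorescing areas may not be found equally often at the two doses. With two targeted sites at 20 mg/kg, one at 10 mg/kg, q=0.95 and ρ=0.2, P(correct) is 0.80–0.87 when 20 mg/kg is better and 0.69–0.77 when 10 mg/kg is better. The pattern in the table reverses.

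**Step 4: leaving targeted sites out.** With the true accuracies, n=30, and m = 2.5 (one of six excluded) or 2 (two excluded):

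| Sites excluded | ρ=0.1 | ρ=0.2 |
|---|---|---|
| 1 | 0.803–0.827 (12 of 12 rows reach 0.80) | 0.789–0.812 (6 of 12) |
| 2 | 0.783–0.806 (3 of 12) | 0.773–0.795 (none) |

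**The case against.** The strongest reply is that fluorescence may never decide a site. Step 1 of 4.4.3.1 has tumor and normal sites identified under white light. Section 8.2 fills all six places by location, and 4.4.3 caps the number at six. Center, edge and adjacent sites might be sampled and some of them simply fluoresce. Step 2 of 4.4.3.1 can mean extra sites or the same sites viewed in both modes. The exact procedure is assigned to the Appendix III flow chart, which is not visible here. On that reading only a conflict of wording remains. This stands as a real possibility, so a reader should not infer that fluorescence-driven sampling is certain. It does not remove the text of 4.4.3, which names fluorescing areas as a site type.

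Second, the selection reason may be partly recoverable. Section 4.4.2 (Surgical treatment) records the biopsy location on the fluorescence image, and 6.1 holds images, coordinates, MR appearance and the surgeon's call. Case report forms are not among the documents, so the gap is verified against 6.1 only. None of the listed items states the reason.

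Third, the sizes depend on assumptions. Overlap shrinks the loss: at half a site with q at PPV, P(correct) when 20 mg/kg is better is 0.776–0.794 (ρ=0.2) or 0.794–0.812 (ρ=0.1). Lower prevalence moves the Youden index further: at 30%, q for true 0.75/0.70 is 0.52 and the apparent Youden is 0.38 (one site) or 0.31 (two) instead of 0.45. For the ROC and probe analyses, where selection is partial, nothing was computed. These limits stand.

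**Conclusion.** The concern holds in a limited form. Section 4.4.3 makes visible fluorescence a stated ground for a biopsy, 8.2 derives its 80% for location-defined sites only, and neither the analyses nor 6.1 tells the two kinds apart. If such sites are pooled, the 80% is not established for that sampling. The mechanism is complete for the score rule and partial for ROC or probe cut-points.

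A reader might infer two stronger conclusions, and the documents support neither. One is that the 80% is wrong or that the trial will miss it: Table 1 reproduces, and the effect depends on targeted counts, overlap and tumor share, none of which is given. The other is that pooling always favors the lower dose: the equal-count scenarios mostly tilt that way, but Step 3 shows the reverse.

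**What to change.** 1. Reconcile sections 4.4.2 (Surgical treatment), 4.4.3, 4.4.3.1 and 8.2 and the Appendix III flow chart on which sites are sampled. If the chart does not already say so, state in step 1 of 4.4.3.1 that primary-analysis sites are marked before fluorescence is viewed. Whether a site is safe to sample stays with the surgeon.
2. Add one field per specimen to 6.1 for how the site was chosen: white light or navigation, fluorescence, or MR.
3. State in 8.1 that the primary sensitivity, specificity, ROC and Youden estimates use sites chosen without regard to fluorescence, which is the sampling 8.2 assumes. Report fluorescence-targeted sites separately as the proportion containing tumor, and give the pooled result as a sensitivity analysis.
4. If targeted sites take up part of the six-site cap, restate the 8.2 probability at n=30 using the values in Step 4.

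The cost is text edits and one data field, with no extra patients or biopsies. There are two downsides. Sites marked under white light are still surgeon-chosen and may under-represent tumor not evident that way, which matters for a program that aims to improve on white light; the separate and pooled reports keep that information. Precision also drops if sites are excluded: at ρ=0.2 the 95% half-width for a sensitivity of 0.75 goes from 0.106 to 0.112 (one excluded) or 0.120 (two).

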5.0 MEASUREMENT OF EFFECT

5.1 ENDPOINTS

Objectives: The endpoints are detection of residual tumor and of normal tissue. The *primary* endpoint will be correspondence between intensity of *in vivo* fluorescence and PpIX concentration and the pathologist's quantification of tumor in biopsy specimens, e.g. percent tumor present. The measures used in the *secondary* objective will be PpIX concentration, $\mu\text{g}/\text{mg}$ and intra-operative fluorescence intensity. Measures used in the *third objective* will be the biopsy specimen's fluorescence intensity and the MR image enhancement at the biopsy site's intraoperative stereotactic coordinates as determined by the surgeon.

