Secondary Objective: We will assess the correlation between the recorded *in vivo* qualitative assessment of fluorescence signal from the neurosurgeon with the post-surgical (i.e., *ex vivo*) absolute PpIX concentration detected in *ex vivo* tissue biopsies. The surgeon will subjectively score the intra-operatively observed fluorescence level as follows: 0, no fluorescence, 1, low fluorescence, 2, moderate fluorescence, or 3, high fluorescence [after 16]. We will first graph fluorescence against each PpIX concentration measurement (intraoperative and *ex vivo*) to evaluate the shape of the relationship. Additionally we will calculate a Spearman's correlation coefficient with 95% confidence interval to assess the correlation between fluorescence against each PpIX concentration measurement (intraoperative and *ex vivo*). The sensitivity and specificity of these observations will be determined [after 16], where the sensitivity of observable intraoperative PpIX fluorescence is the probability of observable intraoperative fluorescence given the presence of tumor cells in the tissue and specificity is the probability of no observable intraoperative fluorescence given that there are no tumor cells in the tissue [16]. We will also explore whether dose, patient, and disease characteristics affect the strength of the relationship between these measurements using multivariable generalized mixed models.

Tertiary Objective: To determine the association between the presence of fluorescence in the surgical cavity and the post-operative image enhancement on MRI. This includes the relationship between the amount and location of residual tumor detected by fluorescence, PpIX concentration, and intra-operative frameless stereotaxy following maximal resection versus the amount and location of tumor imaged post-operatively via CT and/or MRI. Assessment of agreement between fluorescence, intra-operative PpIX concentration, and MR intensity will be explored using the radiologist's assessment of MR intensity, measured on an ordinal scale. A multivariable ordinal logistic model will be fitted to assess the strength of the relationship and whether dose, patient or disease characteristics affect the relationship.

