For each patient, samples will be removed from six sites (2 center of tumor, 2 edge of tumor, and 2 adjacent normal tissue). It is assumed that on average, three samples will be tumor positive based on pathology, and three will be tumor negative. Thus, on average, each subject will contribute 3 true positive samples (used in estimating sensitivity), and 3 true negatives (used in estimating specificity). If n subjects per stratum (new or recurrent) are studied at a given dose, and π and θ are the sensitivity and specificity, we assume that the estimated sensitivity and specificity obtained as the proportions of true positives and true negatives are approximately normally distributed with means π and θ and respective variances $\pi(1-\pi)(1+2\rho)/3n$, and $\theta(1-\theta)(1+2\rho)/3n$, where ρ is the within-subject correlation of binary responses obtained for tissues on the same subject. This formula can be derived for example assuming a beta-binomial model to model extra-binomial variability. Here the term $(1+2\rho)$ is the design effect where the coefficient of ρ is $m-1$, where m is the number of true positive or true negative samples per subject. Given specified values of sensitivity and specificity for the two doses reflecting a scenario where Youden indices differ between doses, the probability that the better dose has the higher observed Youden index can be determined, and the sample size n determined such that this probability is high.

Table 1 below presents required numbers of patients per group in order to have 80% probability of correctly identifying the optimal dose, when the Youden indices of the two doses differ by 0.10, using a range of plausible values for sensitivity and specificity, for intrasubject correlations of $\rho=0.1$ and 0.2. **Based on these results it can be seen that with sample sizes of 30 glioblastoma multiformes (GBMs) there is a 80% or higher**

chance of correctly identifying the optimal dose when Youden indices differ by 0.10 or more. Assuming sample size n=30 and intrasubject correlation $\rho=0.2$, the 95% confidence intervals for $\pi=0.75$, $\theta=0.70$, and youden index=0.45 are (0.64, 0.86), (0.59, 0.81), and (0.23, 0.67), respectively.

Table 1. Required sample size per group to correctly identify the optimal dose with probability of 80%, when Youden indices differ by 0.10 between doses, for various combinations of sensitivity and specificity and intrac-subject correlation, ρ .

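### Some biopsy sites are chosen because they fluoresce and another because it enhances on MR; the tertiary model relates these two variables without allowing for that, so its odds ratio is biased downward where both routes act in the same region

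*Combined protocol and SAP*

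**What the plan says.** **Which sites are sampled.** The pre-operative Section 4.4.3 (patient groups, numbers and ALA dose) says that "biopsies will be taken at up to six sites identified by the surgeon". Its list has three kinds of site:

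- by location: tumor center, tumor edge and, if safe, the surrounding area;
- by fluorescence and by MR enhancement: "areas seen to fluoresce intraoperatively and an area with MR enhancement outside" the tumor region, the MR area again only if safe.

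No number is given for each kind. Section 4.4.3.1 (bulk tumor measurements) also uses fluorescence to find sites: "A biopsy will be taken of each of the sites identified under white light illumination and under fluorescence imaging". Section 4.4.2 (surgical treatment) adds: "Each tissue biopsy will be taken at the discretion of the operating surgeon".

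**A different list.** Section 8.2 says that "samples will be removed from six sites (2 center of tumor, 2 edge of tumor, and 2 adjacent normal tissue"). In that layout no site is chosen for fluorescence or enhancement.

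**What is analysed.** Section 5.1 gives the tertiary measures as "the biopsy specimen's fluorescence intensity and the MR image enhancement at the biopsy site's intraoperative stereotactic coordinates". For this objective Section 8.1 states: "A multivariable ordinal logistic model will be fitted to assess the strength of the relationship". The model may include dose, patient and disease characteristics. It has no term for region or for why a site was sampled. The only adjustment named for all models is robust standard errors for specimens from the same person. None of the eleven data items in Section 6.1 records why a site was chosen.

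**The concern.** The two variables whose association is wanted are also two of the reasons for taking a biopsy. A site that neither fluoresces nor enhances can enter only by location. Sites positive on either variable have an additional way in. In a region where both routes operate, the cell of sites negative on both is therefore under-represented, which produces a negative association between fluorescence and enhancement that tissue biology did not create.

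Robust standard errors change the variance and leave this bias in place. At stake is a tertiary conclusion that fluorescence and MRI agree less well than they do, in the area where residual tumor would be looked for. If the reason for each biopsy is not written down at surgery, it may not be recoverable later.

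**Working it through.** The plan states no odds ratio, sample size or power for the tertiary objective, so there is no figure to reproduce.

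**Inputs.** The kinds of site come from Section 4.4.3. Everything numerical is assumed: the prevalences of fluorescence (pF) and enhancement (pE), the number of sites of each kind, and the true odds ratio. Both variables are reduced to present or absent.

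**Formula.** Per patient, take r location-chosen, kF fluorescence-chosen and kE MR-chosen sites in one region. Let a = kF/pF and b = kE/pE. Relative to its population share, each cell is sampled with weight:

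- positive on both: r + a + b
- fluorescing only: r + a
- enhancing only: r + b
- neither: r

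The sampled odds ratio is the true one times r(r + a + b) / [(r + a)(r + b)]. The multiplier does not depend on the true odds ratio.

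**One route only.** With b = 0 it is r(r + a)/[(r + a)r] = 1. With a = 0 it is likewise 1. The bias needs both routes.

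**Both routes, outside the tumor, kF = kE = 1.** At 30% prevalence a = b = 3.333:

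- r = 1: 7.667/4.333² = 0.41
- r = 2: 2 × 8.667/5.333² = 0.61

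| Prevalence (pF = pE) | r = 1 | r = 2 |
|---|---|---|
| 10% | 21/121 = 0.17 | 44/144 = 0.31 |
| 30% | 0.41 | 0.61 |
| 50% | 5/9 = 0.56 | 12/16 = 0.75 |
| 70% | 0.65 | 0.83 |

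At 30% a true odds ratio of 2 in this subset appears as 0.82 (r = 1) or 1.22 (r = 2). With r = 0 the multiplier is 0, so the figures depend on location-chosen sites being present.

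**Different scans.** Suppose that a site enhancing on the selecting scan also enhances post-operatively with probability 0.3 to 0.8, and any other site with probability 0.1. With one site of each kind and prevalence 30% or 50%, the ratio of sampled to unselected odds ratio is about 0.54 to 0.83. For example, at 0.8 versus 0.1 and 30% prevalence, a true odds ratio of 2 on the selecting scan gives 1.62 unselected and 0.87 sampled; 0.87/1.62 = 0.54.

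**Pooling center and edge sites.** Section 8.1 defines no outside-tumor subset, so pooling matters. Take 30% prevalence outside, r = 1, and a true odds ratio of 2 in every region. Cells are listed as both, fluorescing only, enhancing only, neither.

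- Population shares outside: 0.1218, 0.1782, 0.1782, 0.5218. Multiplied by weights 7.667, 4.333, 4.333 and 1: 0.934, 0.772, 0.772, 0.522.
- Three in-tumor sites, each 60% positive on both measures, add 1.2, 0.6, 0.6, 0.6. The crude odds ratio is 2.134 × 1.122/1.372² = 1.27.
- At 90% positive they add 2.451, 0.249, 0.249, 0.051. The crude odds ratio is 3.384 × 0.5725/1.0216² = 1.86.

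Two errors offset here. Selection pulls the estimate down, while mixing regions pushes it up. With two center sites at 80% or 90%, one edge site at 60% or 70%, and all three outside sites chosen by location, the crude odds ratio is 3.81 or 5.61. With the selected sites it is 1.42 or 1.68.

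**Testing the remedy.** Dropping the MR-chosen site changes the outside cells to 0.528, 0.772, 0.178, 0.522, an odds ratio of 2.00. Pooled with the same three in-tumor sites and no region term, however, it gives 1.81 (60%) to 3.90 (90%). Dropping the site and adding a region term gives 2.00 in every case run.

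**The case against.** The strongest reply is that the plan does not clearly create the biased situation.

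- **Where the fluorescing sites are.** The phrase about lying outside the tumor can be read as applying only to the MR area, and Section 4.4.3.1 takes fluorescence-identified biopsies under a bulk-tumor heading. If all fluorescing sites lie within the tumor, outside sites are chosen by location or MR only and the multiplier is 1.00. This stands as an open reading; the text does not settle it.
- **Section 8.2 has no selected sites.** Under that layout the multiplier is also 1.00. But that is a sample-size assumption, and it conflicts with the procedures in 4.4.3 and 4.4.3.1. It does not override them.
- **Different scans.** A site must be picked from an image available before the biopsy, while Sections 2.4 and 8.1 make post-operative enhancement the outcome. This weakens the bias without removing it. Section 5.1 does not say which scan supplies the measure.
- **The analysis is exploratory.** Section 8.1 says so in substance, and neither the sample size nor the dose choice rests on it. That limits the weight of the point.
- **The arithmetic is simplified.** The plan uses an ordinal MR outcome and graded fluorescence, and the surgeon's discretion means that sites within a kind are not a random sample. The figures are illustrations.

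A reader might infer that choosing sites on either variable alone is harmful, or that the tertiary odds ratio as planned will be cut to 0.4-0.6 of its value and reversed. The first is wrong by the formula. The second applies a figure for outside-tumor sites, with assumed prevalences and one scan for both purposes, to a model that the plan does not restrict to those sites.

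**Conclusion.** The concern holds in a limited form. Section 4.4.3 as written allows selection on both variables of the tertiary model, and neither Section 8.1 nor the robust standard errors deal with it. Where both routes act in the same region, the direction is certain: downward.

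The size is not known from the documents. Under the assumptions shown, the multiplier outside the tumor is about 0.4-0.6 at 30% prevalence and 0.17-0.83 over 10-70%. It is nearer to 1 if the two scans differ, and 1.00 if the fluorescing sites are all inside the tumor. In a pooled model with three center or edge sites, 60-90% positive on both measures, a true odds ratio of 2 appears as about 1.3-1.9. That is attenuated but not reversed, and it comes from two opposing biases, so it should not be taken as reassurance. Because the objective is exploratory, this is a change that should be made, not one on which the trial's main conclusion depends.

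**What to change.** 1. Reconcile the site lists in Sections 4.4.3 and 8.2, and say whether the fluorescing sites may lie inside the tumor, outside it, or both.
2. Record two codes for each biopsy at surgery: its region (center, edge, outside tumor) and why it was chosen (location, fluorescence, MR enhancement). Add both to Section 6.1.
3. State in Section 8.1 that the tertiary model includes a region term and leaves out the MR-chosen site, which is reported separately. Both parts are needed: dropping the site alone leaves confounding by region, and a region term alone leaves the outside-tumor stratum biased.
4. Refit on location-chosen sites only as a sensitivity check.

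The cost is two fields on the biopsy form and a short addition to Section 8.1. The downside is that at most one biopsy per patient leaves this exploratory model: with the 4 × 30 = 120 patients of Table 3 and up to six biopsies each, at most 120 of up to 720. The change does not remove selection by the surgeon within a kind of site, which should be stated as a limitation.
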